The data for each subject will be extracted from her medical record data in Joslin Diabetes Center for statistical analysis by [name]. After abstracting the data, it will be merged via the key with the personal identifiers dataset housed on [name] computer (PI) with questionnaire data by [name] and the Research Assistant. Once this merge takes place, personal identifiers will be removed and only the unique study ID will remain attached to this information. As described in Section 6, the key to the code, linking the subject's personal information to the subject will be kept in a locked file in Joslin Diabetes Center. Only [name] (PI) and [name] RD will have access to the key to the code.

Only the following data from medical records will be sent to the co-investigators for data analysis:

- Height
- Weight immediately before pregnancy
- Weight prior to delivery
- Age at delivery
- Gestational age at delivery
- Race/ethnicity
- Marital status
- Education level
- Family income
- Use of insulin in pregnancy
- Contraceptive use/type
- Gravidity and parity
- Breast feeding exclusively (yes or no)
- Bottle feeding exclusively (yes or no)
- Mixed breast and formula – how many bottles of formula/day
- Breast feeding exclusively duration
- Mixed breast and bottle duration
- Weight at 3 months and 9 months (groups 2 and 3) and 1 year +/- 3 months (all 3 groups)
- 6 week glucose tolerance test results
- 1 year glucose tolerance test results
- Barriers to adherence—healthy eating and physical activity (from questionnaire)
- Partner support
- self-care and –efficacy,
- perception of infant care giving needs,
- knowledge and fear of diabetes diagnosis,
- depressive symptoms (Edinburgh Postpartum Depressive Scale)
- satisfaction with medical care
- self-report of physician referral for postpartum diabetes screening
- History of other pregnancy complications

The co-investigators will not receive the PHI-containing dataset.

Please answer the following questions:

- Will medical history/clinical information be obtained from the subjects' medical records for the purpose of this study? If yes, please list what information will be recorded.

Approved by
JDC/ CHS
CHS#2012-16

YES

- Height
- Weight immediately before pregnancy
- Weight prior to delivery
- Age at delivery
- Gestational age at delivery
- Race/ethnicity
- Use of insulin in pregnancy
- Contraceptive use/type
- Gravidity and parity
- Weight at 3 months and 9 months (groups 2 and 3) and 1 year +/- 3 months (all 3 groups)
- 6 week glucose tolerance test results
- 1 year glucose tolerance test results

- Will information resulting from this study (i.e. results of clinical/research lab tests, etc...) become part of the subjects' medical record or provided to the subject and/or others for clinical purposes? If, no, please list what information will not be given to the subject or recorded in their medical record and why.

NO

- Will subjects' identifiable health information* be shared with others outside of Joslin Diabetes Center? If yes, list whom this information will be shared with (please be specific, include names of collaborators, study sponsor contacts)?

NO

10. OMIT PROCEDURES / LEAVE STUDY:

A subject who wishes to leave the study or not participate in any specific study procedures can inform CITI-certified, IRB-approved study staff at any time. Study participants will be given information, as to how to contact study staff or the Principal Investigator of the study. Written or verbal dissent will be accepted and a note will be included in the study participants file to ensure that all study staff are aware of participants' decision.

11. INCENTIVES / REMUNERATION:

Subjects in group 1 and 2 will receive \$50 for completion of the study while subjects in group 3 will receive additional \$50 for reporting their self- glucose tests done through 3 months- 9 months. If a participant only completes part of the study then the remuneration will be prorated. In addition, those who are randomized to the nutrition/exercise classes will receive reimbursement for parking.

12 months (Groups 1, and 2)	\$50.00 check for completion of study
12 months (Group 3)	\$100.00 check for completion of study

* **Identifiable Health Information**

Approved by
IDC/ CHS
CHS#2012-16

[Signature]

Data that includes any of the following identifiers are considered identifiable health information: ("X" denotes data to be collected)

- Name
- Social Security number
- Medical Record Number
- Address by Street Location
- Address by Town/City/Zip Code
- Date of Birth
- Telephone Number
- Electronic E-Mail Address

Approved by
JDC/ CHS
CHS#2012-16

Please answer the following questions:

Where and how will your project utilize the Joslin Diabetes Center?

General Clinical Research Center (GCRC)
 Clinical Trials Unit (CTU)
 Joslin Clinic
 Eye Unit
 Other (please specify) _____

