Study Population: During the 3rd trimester of pregnancy and up until 3 months postpartum, we will recruit a total of n=30 women (10 women in each group) with GDM or a recent history of GDM, who are seen by clinical staff at the Joslin Diabetes Center/Beth Israel Deaconess Medical Center's (JDC/BIDMC) Diabetes and Pregnancy Program. Study participants would have delivered between June 1, 2012 and May 31, 2016. Recruitment for the study will occur at Joslin Diabetes Center after the second visit for GDM in the Diabetes and Pregnancy Program. A research assistant will provide information about the study, review an informed consent form and offer participation in the study. Potential subjects will be advised that participation is voluntary and should they agree to participate in the study, they will be randomized to 1 of three intervention groups to which they will not have a choice of group assignment.

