The purpose of the 6 weeks to 3 months, and 6, 9, and 12 month web-based questionnaires is to determine the association between barriers to care and postpartum diabetes screening in women with a history of GDM. Specifically, we will evaluate self-care and efficacy, perception of infant care giving needs, fear of diabetes diagnosis, depressive symptoms, as well as access to and satisfaction with medical care. We will also ask women whether or not a physician referred them for diabetes screening. We will also assess women's adherence by asking whether they received diabetes screening (either a fasting glucose or a 2-hour 75 gram oral glucose tolerance test) at 12 months. In addition to collecting this information, we will ask women about their marital status, parity, medical history, breastfeeding behaviors, as well as information on diet (using a validated food frequency questionnaire), and physical activity levels. We will also obtain information on partner and family support. The web-based questionnaire will be on a secure server using Red Cap software available through Harvard Medical School. We will also ask women to report their current weight for each questionnaire. Data on their most recent pregnancy is also available, including total weight gain and blood glucose control during pregnancy.

Laboratory Data:

For women reporting having received diabetes screening, we will ask for authorization to collect the laboratory results from the screening test. The study participant will be mailed an IRB-approved medical authorization and release form requesting data on their postpartum fasting glucose or 2-hour 75 gram

Approved by

JDC/ CHS

CHS#2012-16

oral glucose tolerance test, and most recent postpartum weight, as documented by their primary care physician. Once the medical authorization and release form have been signed and returned to our study team, we will collect information from the ordering physician on either a fasting glucose or a 75 gram 2-hour OGTT, per the study participant's authorized consent, as well as the recent postpartum weight.

Table 1 – Group 1 Standard Care

Contact 1 (Enrollment/ Randomization)	Contact 2 (6 weeks post-partum)	Contact 3 (6 weeks to 3 months post-partum)	Contact 4 (6 months post-partum)	Contact 5 (9 months post-partum)	Contact 6 (12 months post-partum)

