4. DATA ANALYSIS / SUBJECT SELECTION

For aim 1, we will calculate the proportion of women who received postpartum diabetes screening in each group using intention-to-treat analysis. We will calculate the association between the interventions versus standard care by calculating chi-square and p-values to assess statistical significance. For aim 2, we will evaluate the association between our intervention and continuous blood glucose levels among women who received the 12-month 75 gram 2 hour OGTT or glucose. We will use ANOVA to calculate F-statistics and p-values to determine whether the intervention was associated with improved blood glucose levels compared to the standard care. Similarly, for aim 3, we will evaluate the association between our intervention and continuous weight measurements using ANOVA. As a secondary hypothesis, we will use multivariable binomial regression to evaluate the association between age, race/ethnicity, sociodemographic factors, self-care, perceived infant care giving needs, fear of diabetes, and access/satisfaction with medical care, and adherence to postpartum diabetes screening at 12 months. We will calculate risk ratios and 95% confidence intervals, adjusting for potential confounders, including sociodemographic factors. We will primarily assess these results for directionality. We will use SAS version 9.2 (Cary, NC) for all analyses.

The proposed project is a pilot study. Therefore, we anticipate having limited power to detect statistically significant results. However, the direction and magnitude of the associations will provide necessary data required for a larger research study to further improve adherence to diabetes screening guidelines after GDM, as well as potentially improve blood glucose results for women in the first year postpartum and reduce weight retention. As such, this study is clinically significant, given that it may provide insight into how to improve adherence to follow-up diabetes screening and subsequent prevention or delayed diabetes diagnosis. This data analysis will be performed by [name] and [name].

Local Interim Data Analysis/Data Monitoring Plan

Approved by

JDC/ CHS

CHS#2012-16

AP

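### Aim 1 names intention-to-treat, but 12-month screening status depends on the woman's reply, so non-response that differs by arm can distort the group difference in either direction

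*Combined protocol and SAP*

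**What the plan says.** Section 4 (Data Analysis / Subject Selection) defines the Aim 1 analysis: "we will calculate the proportion of women who received postpartum diabetes screening in each group using intention-to-treat analysis". The groups are then compared by "calculating chi-square and p-values to assess statistical significance". Section 4 gives no rule for a woman whose status is unknown, no expected loss and no sensitivity analysis.

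Status is found by asking. Section 1 describes the question at 12 months (+/- 3 months). Section 2, under the questionnaire heading, says: "We will also assess women's adherence by asking whether they received diabetes screening". Laboratory confirmation follows only a positive answer. Section 2, Laboratory Data, reads: "For women reporting having received diabetes screening, we will ask for authorization to collect the laboratory results from the screening test". The release form is then mailed, and results are collected once it is signed and returned.

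The protocol allows for incomplete participation. Section 10: "A subject who wishes to leave the study or not participate in any specific study procedures can inform CITI-certified, IRB-approved study staff at any time". Section 11: "If a participant only completes part of the study then the remuneration will be prorated".

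Section 9 lists 1-year glucose tolerance results among the data taken from the Joslin medical record. It does not list a fasting glucose, and Section 4 does not link the record to Aim 1.

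**The concern.** The outcome is itself a follow-up behaviour, and it is measured by whether the woman responds to study follow-up. Not replying and not being screened are then easily confused. The only described route to an outside record opens after she has reported a test, so it cannot help with a woman who is silent.

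Non-response could well differ by arm. Group 3 has classes, monthly reminders, telephone chasing for meter data and $100 rather than $50. It also carries four finger-sticks a day for four days each month. Women know their assignment.

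Section 4 says that the direction and size of the associations will inform a larger study. Those are the quantities that arm-dependent non-response would alter.

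**Working it through.** **Inputs.** From the documents: 10 women per arm (Section 2, Study Population) and a chi-square test (Section 4). Not in the documents, so assumed: true screening p of 30%, 50% or 70%, the same in both arms; loss L of 10% to 40% per arm; two-sided alpha of 0.05. The plan has no figure of its own to reproduce.

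**Step 1. Who can be classified?** A woman who replies yes is classified, and her result is sought. One who replies no is classified. One who does not reply gets no release form, and is classifiable only if a 1-year glucose tolerance test happens to be in the Joslin record and the analyst chooses to use it. A fasting glucose or a test done elsewhere would be missed.

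**Step 2. Unknown counted as not screened.** If loss is unrelated to screening, the observed proportion is p x (1 - L).

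| True p | Loss, Group 1 v Group 3 | Observed, Group 1 v Group 3 | Gap (Group 3 minus Group 1) |
|---|---|---|---|
| 30% | 30% v 10% | 21% v 27% | +6 points |
| 30% | 40% v 10% | 18% v 27% | +9 |
| 50% | 30% v 10% | 35% v 45% | +10 |
| 50% | 40% v 10% | 30% v 45% | +15 |
| 50% | 10% v 30% | 45% v 35% | -10 |
| 50% | 10% v 40% | 45% v 30% | -15 |
| 50% | 20% v 20% | 40% v 40% | 0 |
| 70% | 30% v 10% | 49% v 63% | +14 |
| 70% | 40% v 10% | 42% v 63% | +21 |

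The true gap is zero in every row. The false risk ratio depends only on the losses: 0.9/0.7 = 1.29 and 0.9/0.6 = 1.50. Equal loss creates no gap when the true rates are equal, but it still lowers a true 50% to 40%.

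**Step 3. Unknown left out.** This is harmless if replying is unrelated to screening within each arm, and misleading otherwise. Suppose 4 of 10 women in Group 1 are lost and 3 of the 6 known were screened. The known-status rate is 3/6 = 50%. The rate in all 10 lies anywhere from 3/10 = 30% (none of the four screened) to 7/10 = 70% (all four screened).

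**Step 4. The rule can decide the sign.** Compare that Group 1 with a Group 3 that has no loss and 5 of 10 screened:

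- unknown = not screened: 5/10 - 3/10 = +20 points
- known status only: 5/10 - 3/6 = 0
- unknown = screened: 5/10 - 7/10 = -20 points

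**Step 5. Effect on the test.** I enumerated all binomial outcomes for an uncorrected two-arm Pearson chi-square with 10 per arm and unknown = not screened. At true 50% in both arms, the false-positive rate is 4.2% with no loss, 6.1% with loss of 30% v 10%, and 8.7% with 40% v 10%. At true 70% it is 3.7%, 8.3% and 13.8%.

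**The case against.** A reader might infer that the plan counts loss to follow-up as non-adherence. It does not say so. Intention-to-treat is named without a definition, and leaving unknowns out is also compatible with the text. What is missing is a rule and a way to establish status.

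A reader might also infer that the bias would favour Group 3, the arm expected to do best. The documents do not settle this. Extra contact and payment may help retention, but the testing burden may harm it. Meter testing ends at 9 months, and all arms share the same questionnaire schedule and 12-month contact. The reversed-loss rows in the table are as admissible as the others.

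Nor is it right that a non-responder can never be classified, since the Joslin record may hold her glucose tolerance test. But that record alone is not an even-handed remedy. Under Section 2, Block Blood Glucose Monitoring, only Group 3 women with high meter readings are sent for laboratory testing at Joslin. Readings run to 9 months, when the 12 +/- 3 month window opens. A Joslin-only lookup could therefore find more tests in Group 3.

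Finally, this is a pilot, and Section 4 says "we anticipate having limited power to detect statistically significant results". That weakens any argument from p-values. It does not weaken the argument about direction and size, which the pilot is meant to supply.

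**Conclusion.** The concern holds as a gap in ascertainment together with an unstated rule for unknown status; the plan does not contain a scoring error. The route to outcome verification depends on a positive reply, so either obvious default lets arm-dependent non-response enter the Aim 1 difference.

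Under the assumptions above, counting unknowns as not screened would create a false gap of 6-9 points at 30% true screening, 10-15 at 50% and 14-21 at 70%, in whichever direction the loss runs. These sizes rest wholly on assumed loss and screening rates, and on loss unrelated to screening. With 10 per arm, one misclassified woman moves her arm's rate by 10 points. The point should be addressed, because the change is small and the affected estimates are what the pilot passes on.

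One limit: consent pages are not in the copy reviewed. If the enrolment consent already authorises release of outside records, the first part of the fix reduces to using that authorisation.

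**What to change.** 1. Ask every woman for the medical-record authorisation at enrolment, before randomisation, rather than by mail after a reported test. Use it to establish 12-month status (glucose tolerance test or fasting glucose, from any provider) by the same rule in all arms, unless she withdraws the authorisation. Do not rely on the Joslin record alone. Report separately any laboratory tests prompted by Group 3 meter readings.
2. In Section 4, state the primary rule for women whose status is still unknown and report their number by arm. Beside the primary result, show the known-status result and the best/worst-case bounds.

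The bounds should describe uncertainty and not act as a pass/fail rule. With 3 unknown in Group 1 and 1 in Group 3, the difference already has a range 3/10 + 1/10 = 40 points wide, so a veto could dismiss most real differences.

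Cost: a consent amendment, record requests for up to 30 women, a few sentences and one table. Some women may hesitate to sign a release up front, and the reported range will look less favourable than a single rate.

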4. Determine to what extent barriers to health impact adherence rates to post partum screening and weight loss targets through a web-based questionnaire collected on the 6 weeks to 3 months, 6, 9, and 12 month questionnaires. These questionnaires will assess whether: lack of self care, perception of high infant care giving needs, fear of diabetes diagnosis and postpartum depressive symptoms, difficulty accessing medical care, dissatisfaction with medical care or primary care physician not recommending screening are associated with poorer adherence to diabetes screening guidelines and weight loss goals.

Study aims are:

1. Determine the extent to which women who receive a postpartum group nutrition intervention and/or block blood glucose testing return for a 12 month (+/- 3 months) follow-up screening for diabetes with either a fasting blood glucose test or a 75 gram 2 hour OGTT compared to women who receive standard care. *We hypothesize that women in Group 3 will be the most likely to return for screening at their 12 month follow-up (+/-3 months).*
2. Determine the extent to which women who choose to have diabetes screening conducted at 12 months postpartum and who receive a postpartum group nutrition counseling intervention and/or block blood glucose testing are more likely to have fasting glucose or a 75 gram 2 hour OGTT results within normal range at 12 months (+/- 3months) compared to women who receive standard care.
3. Determine the extent to which women who receive a postpartum on-line nutrition and physical activity counseling intervention and/or block blood glucose testing will meet postpartum weight goals at 12 months postpartum (i.e. more likely to lose 7% of their pre-pregnancy body weight if

Approved by

JDC/ CHS

CHS#2012-16

MM

Date: 03/10/2014

they have a BMI ≥ 25 or return to their pre-pregnancy weight if their BMI < 25) compared to women who receive standard care.

2 STUDY DESIGN:

METHODS:

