Proposed Study Design: This is a pilot study, where we propose to conduct a 3-grouped randomized controlled trial to evaluate whether a 1 ½ to 2 hour on-line nutrition and physical activity intervention +/- block testing of blood glucoses fasting and 2 hours after each meal for 4 days/month from starting at 3 months postpartum and concluding at 9 months postpartum will 1) improve adherence to the receipt of diabetes screening at 12 months postpartum through the recommended 75 gram 2 hour glucose tolerance test or fasting blood glucose test, 2) lower glucose values on the 75 gram 2 hour oral glucose tolerance test or fasting blood glucose test and 3) improve attainment of weight loss targets among women with a recent history of GDM. Patients will participate in an online nutrition and physical activity class at 6 weeks to 3 months and 9 months for women assigned to both groups 2 and 3. For those women assigned to group 3, they will also do block testing using an assigned blood glucose meter and test strips 4 times a day for 4 consecutive days each month, starting at 3 months and ending at 9 months. Women will have the option of submitting meter BG data via e-mailed logs or downloading directly to the clinic using Diasend software. More information about this will be discussed below. Once downloaded, the Diasend software creates a PDF document with all recorded blood glucose values. For purposes of this study, we will obtain a Diasend account specific to this study, which will allow women to download blood glucose information with an anonymous unique identifier that can be accessed by the study's Principal Investigator and CITI-certified, IRB-approved research assistant. Upon accessing the PDF document with the blood glucose meter information, both the PI and the Research Assistant can link blood glucose data with questionnaire and other health information collected in this study through the unique identifiers. More information about the security of the account and linking of data is provided below in Section 6.

On-line Nutrition and Physical Activity Counseling:

The nutrition and physical activity topics for groups 2 and 3, which will be taught using a web-based platform will include the following information by nutrition visit. Diet and exercise interventions will be flexible and sensitive to cultural differences.

6 weeks to 3-month on-line class:

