Women with gestational diabetes who have seen a Joslin Diabetes Center Diabetes and Pregnancy Program provider at least two times during their pregnancy between June 2012 and May 2016 will either be approached during a scheduled clinic visit or contacted by telephone by their provider (also co-investigator) or the Research Assistant. If interested in learning more about the study, the CITI-certified, IRB-approved Research Assistant will be introduced to the woman and will take the woman into a private room where the Research Assistant will describe the study in further detail. The Research Assistant will meet with the potential study candidate, inform the woman about the purpose of the study, as well as provide a brief description of the study design and outcome measures. Women will also be informed of possible benefits and risks of the study. At this time, the Research Assistant will obtain verbal consent to conduct the screening questionnaire to determine a woman's eligibility. If a woman is eligible, she will receive a study participant letter further describing the purpose of the study, as well as the informed consent form to which CITI-certified, IRB-approved Research Assistant will briefly review with the potential study participant. Each woman will be given time to review it before signing. During the review, if the eligible subject has any questions regarding the study, she can raise them with the CITI-certified, IRB-approved Research Assistant or the Principal Investigator. If the eligible subject wishes to bring the consent form home for review, she will be allowed to do so and will be asked to bring the form back on her next visit to Joslin for signing after further clarification of any queries. As mentioned above, the study participant will then receive a copy of the signed informed consent and will be enrolled into the study. At this time, we will use block randomization, using a random number generator to assign women into one of the three study groups. Block randomization will ensure an equal distribution of women into each arm. Women will not have the option of choosing their assignment. They will also not be blind to which group they have been assigned to for participation in the study.

Approved by
JDC/ CHS
CHS#2012-16

9. RIGHTS AND PRIVACY:

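### Aims 2 and 3 name an ANOVA F-test but no comparison with standard care, no mean difference and no interval

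*Combined protocol and SAP*

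**What the plan says.** Section 2 (Proposed Study Design) states that "we propose to conduct a 3-grouped randomized controlled trial". The groups are standard care (Group 1), online class (Group 2), and online class plus block glucose testing (Group 3). Section 2 (Study Population) sets 30 women, 10 per group, and Section 8 says "Block randomization will ensure an equal distribution of women into each arm".

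The study aims in Section 1 are framed against standard care. Aim 2 asks whether women who receive an intervention "are more likely to have fasting glucose or a 75 gram 2 hour OGTT results within normal range at 12 months". Aim 3 asks to what extent they "will meet postpartum weight goals at 12 months postpartum".

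Section 4 gives the analysis. For aim 2 it plans "ANOVA to calculate F-statistics and p-values to determine whether the intervention was associated with improved blood glucose levels compared to the standard care", among women who had the 12-month test. For aim 3 it adds: "Similarly, for aim 3, we will evaluate the association between our intervention and continuous weight measurements using ANOVA". It names no contrast, pairwise comparison, pooling of Groups 2 and 3, mean difference or interval for either aim. Risk ratios with 95% confidence intervals appear only for the secondary regression on screening adherence. The means and standard deviations under the interim monitoring heading are data-quality checks. Section 4 also says that power will be limited and that the direction and size of the associations will inform a larger study.

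**The concern.** The plan asks a directional question against a named reference group and answers it with a statistic that, in a three-group layout, has neither. The three-level F-test asks only whether all three means are equal. It can be significant because Groups 2 and 3 differ from each other, or because an intervention group did worse than standard care.

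Two things are at stake. Followed as written, a significant F could be reported as improvement over standard care when that comparison was never made. And the quantity that a larger study would need, an effect against standard care with its uncertainty, is not among the named outputs for these aims. Section 4 also speaks of a single intervention where the design has two, so the reader cannot tell which comparison is meant.

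**Working it through.** **Inputs.** From the documents: three groups, 10 per group as the maximum, equal allocation, and aim 2 restricted to women who were tested. The documents give no alpha, SD or effect size for these aims. I assume alpha 0.05 (two-sided for contrasts), a 95% confidence level, a common SD, and the means shown. The plan has no figure of its own to reproduce here.

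**Formulas** (n per group, three groups, residual df = 3(n − 1)):
- F = n × (sample variance of the three group means) / SD², on 2 and 3(n − 1) df
- t for one intervention group against standard care = difference / (SD × √(2/n))
- 95% half-width in SD units = t(0.975, df) × √(2/n)

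**Check 1: reference group.** Take means 95 (Group 1), 100 (Group 2) and 90 (Group 3), SD 8, n = 10.
- The variance of the means is (0² + 5² + 5²)/2 = 25, so F = 10 × 25/64 = 3.91 on 2 and 27 df, p = 0.032.
- Each intervention group against standard care: |t| = 5/(8 × 0.4472) = 1.40, p = 0.17. The half-width is 0.918 × 8 = 7.3, so the differences are +5 (−2.3 to 12.3) and −5 (−12.3 to 2.3).
- If Groups 2 and 3 are pooled, their mean is (100 + 90)/2 = 95 and the difference from standard care is 0.

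So the same data are significant under one reading of the plan and show no difference at all under the other.

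**Check 2: direction.** Means 95/87/87 and 95/103/103 with SD 8 and n = 10 both have a variance of means of 21.33. Both give F = 10 × 21.33/64 = 3.33, p = 0.051. Lower and higher glucose in both intervention groups produce the same statistic.

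**Check 3: how often it could matter.** Suppose Group 2 is truly 0.75 SD worse and Group 3 truly 0.75 SD better than standard care. In 100,000 simulated trials with n = 10, F was significant in 82%. Among those, 39% had neither group different from standard care by Dunnett's test, and 67% had no significant improvement in either group. This scenario was chosen to expose the problem; it is not a forecast.

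**Check 4: precision of the missing estimate.**
- n = 10 per group: 2.0518 × √(2/10) = 2.0518 × 0.4472 = 0.92 SD.
- n = 5 per group: 2.1788 × √(2/5) = 2.1788 × 0.6325 = 1.38 SD.

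Ten per group is a ceiling for aim 2. The documents give no expected number tested, so 5 is an assumed lower case.

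**Check 5: multiplicity.** With n = 10, two unadjusted comparisons with standard care at 0.05 have a simulated family-wise error of about 9.0%. Dunnett's critical |t| is about 2.34, against 2.05 unadjusted.

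**The case against.** The best defence is that Section 4 does not say how many levels the ANOVA has. Its singular wording would fit Groups 2 and 3 pooled against standard care. In that case F on 1 and 28 df equals t², and with the sign of the difference it answers the question. This stands as a possible reading. But the plan does not state it, the design has three groups, and the aims refer to the class and/or glucose testing. The comparison needs stating either way.

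Second, this is a declared pilot that expects limited power and puts weight on direction and size, so the investigators would presumably look at the group means. That softens the consequence. It does not remove the gap, because the estimates that would carry direction and size are not named.

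Three stronger readings are tempting, and the documents do not support them:
- A reader might infer that ANOVA cannot answer these aims, or that a non-significant F leaves nothing usable. The limit applies to the F-statistic and its p-value alone. Group means, differences and intervals come from the same model whatever F shows.
- A reader might infer that the F-test should go because contrasts have more power. That depends on the assumed effects and on adjustment. For true effects of 0, 0.4 and 0.8 SD with n = 10, F and the Dunnett-adjusted Group 3 against Group 1 comparison both have power of about 0.31. The case rests on interpretation, not efficiency.
- A reader might infer that Group 3 against Group 1 should lead. The aims single out Group 3 only for return to screening (aim 1), not for glucose or weight.

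**Conclusion.** The concern holds as a gap in specification. For aims 2 and 3 the plan does not name the comparison with standard care, its estimate or its interval. If the ANOVA has three levels, which the design implies but Section 4 does not state, a significant F does not establish that either intervention group improved on standard care.

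The half-width of the missing interval would be about 0.92 SD at best and about 1.38 SD with 5 per group, so the results will be imprecise however they are analysed. The logical point needs no assumed effect size. The numerical illustrations rest on the assumed alpha, SD and means. The change should be made: the rule as written can lead to a wrong statement, and it is cheap to correct. It does not call the design or the data collection into question.

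**What to change.** In Section 4, state that the ANOVA has three levels. From that linear model, report the Group 2 minus Group 1 and Group 3 minus Group 1 mean differences with 95% confidence intervals, for glucose and for weight. Group 3 minus Group 2 may be shown as descriptive only. Say that any statement of improvement over standard care will rest on these differences, not on the F p-value. If p-values are reported for the two comparisons with standard care, name Dunnett's method or a fixed testing order. If a pooled comparison is what the investigators intend, say so explicitly. Give the number analysed in each group beside every aim 2 estimate.

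The cost is a sentence or two in Section 4 and a few estimate statements in SAS, with no new data. The downside is slightly more analysis, and wide intervals shown openly.
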